Research Repositories: If the purpose of this submission is to establish a Research Repository (bank, registry) indicate whether the material you plan to collect would or would not be available from a commercial supplier, clinical lab, or established IRB approved research repository. Provide scientific justification for establishment of an additional repository collecting duplicate material. Describe the repository design and operating procedures. For relevant information to include, see the UK Research Biospecimen Bank Guidance [\[PDF\]](#) or the UK Research Registry Guidance [\[PDF\]](#)

Patient recruitment will be done for the first 42 months of the study after administrative startup (Figure 2). Biochemical measurements, MDCT, QCT and DXA scans, and clinical assessment will be performed at baseline, 6 months, and at 12 months, 18 months and 24 months. Treatment monitoring visits with blood draws (initially bi-weekly or monthly and thereafter every 3 months) and adverse event monitoring phone calls (monthly at least) will occur during years one through five. Interim analyses and first publications will be done once 50% of patients have completed 1 year visits, approximately at the end of Year 3. Final analyses of the data and preparation of abstracts and manuscripts of the obtained results will be completed during year 5. Control patients who completed 1 year of follow up without treatment will be offered additional 2 years of enrollment with treatment according to protocol. Patients who were initially randomized to treatment groups will be offered continued treatment for an additional 1 year to complete 2 years of therapy. Previously enrolled patients will be recruited from the beginning of patient enrollment. These patients will be provided with an additional consent for the extension of the treatment arm.

Figure 2: Study Timeline

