- A compelling rationale for proposed exclusion of any sex/gender or racial/ethnic group;
- The proposed dates of enrollment (beginning and end);
- The proposed sample composition of subjects.

You may reference grant application/sponsor's relevant protocol pages and attach as an appendix using the below attachment button, however, a summary paragraph must be provided in the text box below.

It is anticipated that 990 CKD-5D patients will be enrolled. The study population will include men and women age 21 years and over from various ethnic backgrounds. The enrollment will be done between January 2015 and January 202119.

TARGETED/PLANNED ENROLLMENT: Number of Subjects

Ethnic Category Sex/Gender

Females Males Total

Hispanic or Latino 15 15 30

Not Hispanic or Latino 480 480 960

Ethnic Category: Total of All Subjects * 495 495 990

Racial Categories

American Indian/Alaska Native

Asian 3 3 6

Native Hawaiian or Other Pacific Islander

Black or African American 225 225 450

White 267 267 534

Racial Categories: Total of All Subjects * 495 495 990

Inclusion Criteria:

- Aged 21 years or older;
- Chronic maintenance dialysis of at least 3 months' duration;
- Mental competence;
- Willingness to participate in the study;
- Normal corrected serum calcium.
- Low bone densityOsteoporosis by DXA scan in any site. (T-score = -1-2.5 for men over age 50 or postmenopausal women, or Z-score = --12.5 for all others).

Exclusion criteria:

- Pregnancy or Breast Feeding;
- Incarceration
- Systemic illnesses or organ diseases that may affect bone (except type 1 or type 2 diabetes mellitus);
- Clinical condition that may limit study participation (e.g., unstable angina, respiratory distress, infections).
- Chronic alcoholism and/or drug addiction;
- Known Paget 's disease of bone;
- Prior external beam or implant radiation therapy involving the skeleton, only if randomized to the Teriparatide treatment
- Participation in a study of an investigational drug during the past 90 days;
- Planning to move out of the area within 1 year of the study;
- Scheduled for renal transplantation
- BMD T-score of the radius less than -3.5 by DXA. (if randomized to teriparatide to avoid the known potential negative effects of teriparatide treatment on BMD of the radius)
- Current treatment with medicines containing digoxin;
- More than 3 CT scans in the prior 12 months (to avoid excessive radiation exposure);
- Planned or anticipated oral surgery within the next 12 24 months;

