The study coordinators will approach via phone during normal business hours all patients who completed study participation and those currently enrolled in ROD III to discuss the extended enrollment option. All previous patients will be eligible for approaching for the extension regardless of when initial participation was completed. Patients will be informed about the goals and the protocol of the study. A list of screened patients will be kept under lock and key in the study coordinators office and on a password protected computer.

Advertising: Specify if any advertising will be performed. If yes, please see ["IRB Application Instructions - Advertisements"](#) for instructions on attaching copies of the information to be used in flyers or advertisements. Advertisements must be reviewed and approved by the IRB prior to use. For additional details, see topic "Recruitment of Subjects/Advertising" on ORI's [IRB Survival Handbook](#) web page for the *PI Guide to Identification and Recruitment of Human Subjects for Research* [D7.0000] document [\[PDF\]](#). If you will be recruiting subjects via advertising at non-UK owned or operated sites, you should include a copy of written permission from that site to place the advertisement in their facilities.

Note: Print and media advertisements that will be presented to the public also require review by [UK Public Relations \(PR\)](#) to ensure compliance with UK graphic standards, and equal opportunity language. [i](#)

Print advertisements: The study may recruit subjects through flyers, brochures, posters, cards for clinic rooms, Research Spotlights, bookmarks placed on campus and in the surrounding community and region, including but not limited to the UK Medical Center, UK Clinics, Good Samaritan Hospital, student center, UHS, the 5 UK Center for Clinical and Translational Research wall mounts, Cardinal Hill, monitor screens, and area facilities and businesses.

This study may use physician referral letters to community physicians for patient recruitment.

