Patients consenting for baseline measurements will have BMD measurements of the total hip, lumbar spine and radius by DXA and total body scan. We do not use QCT for initial BMD assessment to avoid unnecessary radiation exposure to patients with normal bone mass who will be excluded from the study. Patients who are not do not have low bone densityosteoporotic by DXA T-scores/Z-

scores at any site will be excluded from further participation. Results from our prior funding period study indicate this will be 30% or 178 patients. Those patients who are identified as having low bone density/osteoporotic will have blood draws performed for determination of turnover status (PTH, PTH ratio and TRAP-5b; see Table 1) and baseline biochemical results (serum calcium and BSAP). They will also have BMD measurements of the total hip and spine by QCT, and CAVC measured by MDCT. Patients will be assigned to one of two treatment arms based on their turnover status: 1) low turnover patients and 2) normal or high turnover patients. For each treatment arm we will use adaptive randomization by group completion rates, age race and gender to assign patients to one of two groups A) treatment, and B) no study treatment (standard of care) controls.

For the extension of treatment modification, we will contact all patients who completed one year in either the treatment or control arms. Patients who previously participated in the treatment arm will be offered an additional 1 year of therapy to complete 2 years of therapy. For patients who previously participated in the control arm, they will be offered 2 years of therapy. Both therapies can be given in two consecutive years, or with a time-gap in-between.

TREATMENT PROTOCOLS:

Low Turnover Groups: Patients with low bone turnover will be randomized to receive daily teriparatide injections with cinacalcet or no study treatment, i.e. standard of care, as controls.

Normal or High Turnover Groups: Patients with normal or high bone turnover will be randomized to receive alendronate or no study treatment, i.e., standard of care, as controls. Teriparatide is not justified in these patients because it might worsen underlying high turnover abnormalities and requires avoidable daily injections.

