Teriparatide for patients with low bone turnover: Patients with increased baseline risk of osteosarcoma will be excluded from this study (Paget's disease of bone, pediatric populations and young adults with open epiphyses, or prior external beam or implant radiation therapy). Our inclusion/exclusion criteria eliminate all of these patients. There are no direct contraindications given for CKD patients given in the package inserts and the safety web page. However, because bone loss with CKD-5D is not specifically addressed in the indications, we have obtained an IND (Investigational New Drug) from the FDA.

If during the monthly monitoring calls/visits or quarterly visits patients complain of new onset adverse reactions such as arthralgia, pain, nausea, dizziness or leg cramps, the patients will be counseled regarding standard treatment measures. Follow-up contact will be made in one week and if symptoms persist, treatment will be discontinued until the next regularly scheduled quarterly monitoring visit. Follow-up communication will occur within 1 week +/- 3 days and if problems persist despite discontinuation, patients will be referred to his/her primary care provider.

If patients complain of injection site reactions, they will be counseled regarding their injection technique and follow-up contact will be made in one week +/- 3 days. If reactions persist, treatment will be discontinued until next regularly scheduled quarterly monitoring visit. If problems persist despite discontinuation, patients will be referred to his/her primary care provider and their participation in the study will end.

In the rare case where PTH level maintenance requires cinacalcet doses that induce serum calcium levels below 8.5 mg/dL, treatment will cease and patients will be excluded from further participation in the study.

Alendronate for patients with normal or high bone turnover: Our inclusion/exclusion criteria cover all of the above-mentioned contraindications. To be safe, we have obtained an IND from the FDA.

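### Two exclusions tied to being randomised to teriparatide miss former low-turnover controls who start it in the extension, and the radiation one contradicts the safety section

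*Combined protocol and SAP*

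**What the plan says.** The exclusion list under Study Population contains two criteria that depend on treatment. One is "Prior external beam or implant radiation therapy involving the skeleton, only if randomized to the Teriparatide treatment". The other is "BMD T-score of the radius less than -3.5 by DXA. (if randomized to teriparatide to avoid the known potential negative effects", and the same line gives its purpose: "to avoid the known potential negative effects of teriparatide treatment on BMD of the radius". The Paget's disease exclusion in the same list carries no such condition.

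Research Procedures splits patients by bone turnover. Low-turnover patients are randomised to teriparatide with cinacalcet or to no study treatment. Normal- and high-turnover patients are randomised to alendronate or to no study treatment.

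Three places describe the extension for controls:
- Study Design: "Control patients who completed 1 year of follow up without treatment will be offered additional 2 years of enrollment with treatment according to protocol".
- Research Procedures: "For patients who previously participated in the control arm, they will be offered 2 years of therapy", followed by "Both therapies can be given in two consecutive years, or with a time-gap in-between".
- Subject Recruitment Methods: "All previous patients will be eligible for approaching for the extension regardless of when initial participation was completed".

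Safety Precautions, in its teriparatide paragraph, says "Patients with increased baseline risk of osteosarcoma will be excluded from this study". It names prior radiation among the conditions meant and asserts that the eligibility criteria already remove every such patient.

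**The concern.** A rule that protects patients from a drug should be triggered by receiving the drug. Here the trigger is the result of the randomisation. A low-turnover control with a radius T-score below -3.5, or with earlier skeletal radiation, is properly enrolled as a control and can later be offered teriparatide without the rule applying. The stated reason for the radius criterion covers that patient just as well as one allocated teriparatide on day one. For radiation the issue is osteosarcoma, which Potential Risks treats as the main worry with this drug.

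There is a second, conditional consequence. If a patient's eligibility depends on which group was drawn, patients with the same baseline can stay in one group and leave the other. The comparison exposed would be the low-turnover comparison of change in total-hip QCT BMD, the primary endpoint.

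**Working it through.** The plan attaches no figure to this point, so there is nothing to reproduce. The main check is of the text.

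**1. Follow one patient.** Take a low-turnover patient with a screening radius T-score below -3.5.
- Allocated teriparatide: the radius exclusion applies.
- Allocated control: the exclusion does not apply, and the patient completes the year.
- Extension: the patient is offered two years of therapy, which for low turnover is teriparatide. The patient was not randomised to it, so the exclusion still does not apply.

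No supplied section describes a re-check of radius T-score or radiation history before extension treatment. Safety Precautions carries the standard of informed consent over to the extension, but says nothing there about eligibility. Normal- and high-turnover controls are not affected, because their therapy would be alendronate.

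**2. Compare the two radiation rules.** Study Population limits the radiation exclusion to patients randomised to teriparatide. Safety Precautions excludes such patients from the whole study and says the criteria achieve this. As worded, they do not. If Safety Precautions governs, the radiation gap closes and only the contradiction remains. The radius criterion has no matching text.

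**3. Is the information available in time?** Yes.
- Radius DXA is part of the screening measurements (Research Procedures).
- Medical history is recorded (Research Materials).
- Turnover status is known before treatment consent (Safety Precautions).
- DXA, which includes the distal radius, is repeated at 12 months (Study Design).

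**4. Conditional bias, as illustration only.** All inputs are assumed. The documents give neither the affected share, nor how those patients' hip BMD changes, nor the low-turnover group size. Let q be the affected share, d their mean one-year hip BMD change minus that of the rest (in SD), and n the number randomised per group. Assume no true treatment effect and removal of affected patients from the teriparatide group only.
- Bias (treated minus control) = -q × d.
- SE = √[1/(n(1-q)) + (1 + q(1-q)d²)/n].
- Example: q = 0.10, d = 0.5 in absolute value, n = 100. The bias is 0.05 SD in absolute value. SE = √(1/90 + 1.0225/100) = 0.146, and the ratio is 0.342. Two-sided type I error = Φ(-1.96 - 0.342) + Φ(-1.96 + 0.342) = 6.4%.

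The results below are for n from 50 to 150:

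| q | d (absolute) | Bias (SD, absolute) | Type I error |
|---|---|---|---|
| 2% | 0.5 | 0.010 | 5.0% to 5.1% |
| 5% | 0.5 | 0.025 | 5.2% to 5.5% |
| 10% | 0.5 | 0.050 | 5.7% to 7.0% |
| 20% | 0.5 | 0.100 | 7.5% to 12.8% |

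The direction reverses with the sign of d. If affected patients lose more bone, dropping them from the treated group favours teriparatide. If they lose less, it works against it. If all patients are analysed as randomised, the bias is zero.

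**The case against.** The strongest reply is that the sponsor probably meant the low-turnover arm. Research Procedures calls the turnover strata treatment arms. Research Procedures and Safety Precautions both describe criteria being met before patients are approached, and the radius DXA comes before treatment consent. On that reading the condition only spares patients bound for alendronate, and both problems vanish. This is a plausible intention, but the exclusion list does not say it, and Research Procedures uses randomisation for the draw between teriparatide and no study treatment.

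The extension text offers former controls treatment according to protocol, which could be read as carrying the eligibility limits along. That does not help, because the protocol's own limit is tied to randomisation. It is fair to add that previous patients are said to be eligible only for being approached, and that the extension consent and the attached figures are not in the supplied text. The absence of a re-check is therefore established only for what can be seen.

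A reader might infer that the low-turnover comparison is biased as planned. The documents do not support that. No section describes removing a patient after randomisation, and every input to the illustration above is assumed. Nor does the absence of an as-randomised statement prove it: the supplied text defines no analysis population for any comparison, which is a separate and general gap.

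A reader might also infer that patients with prior radiation are certain to be given teriparatide. Safety Precautions says the opposite. What can be shown is a contradiction.

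**Conclusion.** The point holds as a wording fault with a safety consequence. As written, the radius exclusion does not reach a former low-turnover control who starts teriparatide in the extension, and no other supplied text does so. On radiation, Study Population and Safety Precautions cannot both be right. The number of patients concerned is not given and cannot be derived.

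The selection-bias part is conditional. It arises only if the criteria are applied after allocation and affected patients are left out of the teriparatide group alone. Its size and direction are then unknown. With assumed shares of 2% to 5% and differences up to 0.5 SD, type I error stays at or below 5.5%, so it may be negligible. It would not by itself justify an amendment. The safety gap should be fixed. Confidence is medium, because the sponsor may have meant the whole low-turnover arm and the extension consent is not visible.

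**What to change.** 1. Replace the condition in both criteria with *if classified as low turnover*. Apply them to every low-turnover patient before randomisation, using the screening radius DXA and the recorded history. Do not simply delete the conditions: that would also exclude normal- and high-turnover patients, who are never given teriparatide and whom the present wording keeps eligible.
2. Make Study Population and Safety Precautions say the same thing on radiation.
3. Before any former low-turnover control starts teriparatide, re-check radiation history and the latest radius T-score. Use the 12-month DXA, or a new DXA only if there has been a time gap.
4. Enrolment was planned from January 2015, so some patients will already have been randomised. Analyse them as randomised. If any treated patient was removed under these criteria and has no outcome, remove patients meeting the same baseline criteria from both groups.

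The cost is a short amendment, one check at extension entry and one sentence on the analysis set. A few low-turnover patients will not be randomised or not be offered extension teriparatide, and an occasional repeat radius DXA will be needed. If removal from both groups is required, the standard error rises by the factor 1/√(1-q). That is about 1.0%, 2.6%, 5.4% or 11.8% at assumed affected shares of 2%, 5%, 10% or 20%.

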Treatment Protocol for Teriparatide: Patients with low bone turnover will receive a starting dose of 20 µg teriparatide per day via subcutaneous injections along with 30 mg of cinacalcet p.o. daily in the evening will be added after two weeks if PTH is greater than 200 pg/mL at the first biweekly lab draw. Teriparatide treatment alone in patients with histologically proven low turnover bone disease did not result in an increase in bone formation markers.²⁵ Concomitant treatment with cinacalcet is needed in these patients when intact PTH is above 200 pg/mL. To monitor control of PTH and serum calcium levels we will measure them initially one week +/- 3 days after treatment then at the biweekly monitoring visits at the CCTS and quarterly thereafter. Teriparatide dosage will be adjusted according to changes in serum calcium. If serum calcium is between 10.2 and 11 mg/dL, frequency of injection will be reduced to 5 of 7 days per week (non-injection days should not be consecutive and blood draws for serum calcium should be the morning after an injection day). A follow-up visit with serum calcium check will be scheduled in two weeks +/- 3 days. If at that time calcium levels are still between 10.2 and 11, patients will remain with injections on 5 of 7 days per week. If calcium levels return to below 10.2 mg/dL, daily injections will be reinstated and quarterly calcium checks will be performed. If serum calcium is greater than 11.0 mg/dL, treatment will be withheld for two weeks at which time serum calcium will be rechecked. If it is between 10.2 and 11.0 mg/dL we will reinstitute treatment at the reduced frequency of 5 of 7 days per week. If calcium remains above 11.0 mg/dL, patients will be referred to their primary nephrologist for workup of their hypercalcemia and excluded from further participation in the study.

To assess response or compliance to teriparatide, BSAP (see Table 2) will be measured bi-weekly until steady-state and quarterly thereafter. If results do not increase at least 8% (largest inter-assay error of this marker) the study coordinators will carefully review with the patients the technique of injections and possible compliance lapses. There are no known critical levels indicating undesirably high response without concomitant hypercalcemia. Patients, and if needed a caregiver, will be trained in the subcutaneous administration of teriparatide according to the manufacturer's guidelines.

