Table 2. Detail of Blood Draws for Monitoring Safety and Compliance and Secondary Endpoint Serum Biochemical Parameters
Teriparatide

Treatment Group Base-line Bi-weekly visits until steady state Q1 Visit Q2 Visit Q3 Visit 1 Year 15 mo 18mo 21mo 2 yr
or Safety: Serum Calcium & PTH X X X X X X X X X X X X

For Compliance: BSAP X X X X X X X X X X

Secondary Endpoints: FGF23, P1NP, Sclerostin, DKK-1 & PTH Ratio X X X X X

Alendronate

Treatment Group Base-line Monthly visits until steady state Q1 Visit Q2 Visit Q3 Visit 1 Year 15 mo 18mo 21mo 2yr

For Safety and Compliance: BSAP X X X X X X X X X X

Secondary Endpoints: Serum Calcium, PTH & PTH Ratio, FGF23, P1NP, Sclerostin, DKK-1 X X X X X

Standard of Care Controls Base-line Q2 Visit 1 Year 15mo 18mo 21mo 2 yr

Secondary Endpoints: All of the above Serum Biochemical Parameters X X X X X

Cinacalcet will be adjusted in 30 mg steps up to a maximum daily dose of 180 mg if needed to keep intact PTH at levels less than 200 pg/mL. If by six weeks, this fails to achieve PTH levels less than 200 pg/mL, patients will be excluded from further study participation. In the rare case where PTH level maintenance requires cinacalcet doses that induce serum calcium levels below 8.5 mg/dL, treatment will cease for two weeks after which calcium will be re-measured. At two weeks if calcium remains below 8.5 mg/dL, patients will be excluded from further participation in the study. If calcium is normalized, cinacalcet will be reinstated at half of the prior dose. Calcium will be checked again at the next monitoring visit. If at any measurement point PTH levels are less than 60 pg/mL cinacalcet will be withheld and reinstated if levels are again above 200 pg/mL.

Treatment Protocol for Alendronate: Patients with normal or high bone turnover will receive a starting dose of 35 mg alendronate p.o. once per week. Patients will be carefully instructed to follow the manufacturer's recommendations for administration. Serum calcium will be rechecked 1 week +/- 3 days after starting therapy. Dosage will be adjusted according to changes in the bone turnover marker

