Treatment Consent Once bone turnover status has been determined, patients will be approached for the second consent form addressing treatment. It will again be emphasized that willingness or unwillingness to participate in any aspect of the proposed studies will not affect the patients' medical care. The protocol will be presented by the study coordinators supported by the PI where needed and the patients will be given ample time to think about their participation and to discuss participation with their primary nephrologist, other treating physicians, or any other persons. After agreement to participate, the second written treatment consent form approved by the IRB of the University of Kentucky will be signed by each patient. One copy of the first and second signed consent form will be given to the patient; another will be kept in the study coordinators' office under lock and key.

Expanded Consent Patients who have previously completed one year of therapy or standard of care or are currently enrolled will be re-approached for a third consent to extend the treatment so that two years of medication therapy will be completed. The same standard of informed consent will apply to the treatment extension consent.

Protection against risks The PI is a nephrologist who specializes in bone and mineral disorders and renal osteodystrophy. All personnel involved in the research have passed or will pass the test "Protection of Human Subjects in Research," by the Collaborative Institutional Training Initiative (CITI) at the University of Miami. All investigators and key personnel have received or will receive training for the Health Insurance Portability and Accountability Act (HIPAA) (levels 1 and 2).

Monthly and quarterly monitoring: Monthly telephone or personal contact will be made by the study coordinators to the patients in order to monitor possible adverse events or reactions. Thereafter, every three months, patients will be seen by the study coordinators who will perform a general health assessment. At these monitoring visits, there will be blood draws for monitoring safety. The PI will be available at all times for phone consultation via cell phone and/or a 1-800 telephone number of the University of Kentucky Healthcare written on the consent forms.

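### The return from 5-of-7 to daily teriparatide triggers no calcium check; two neighbouring calcium rules also need tidying

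*Combined protocol and SAP*

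**What the plan says.** Under Research Procedures, Treatment Protocol for Teriparatide, patients start on 20 µg daily. For calcium and PTH, "we will measure them initially one week +/- 3 days after treatment then at the biweekly monitoring visits", with quarterly measurement after that. Table 2 labels the early phase "Bi-weekly visits until steady state" and gives it no duration; the fixed visits Q1, Q2, Q3, 1 year and so on follow.

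The rules for raised calcium are:

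- **10.2 to 11 mg/dL:** injections drop to 5 of 7 days, and "A follow-up visit with serum calcium check will be scheduled in two weeks +/- 3 days." Blood for calcium is to be taken the morning after an injection. If the value is still in this range, the patient stays on 5 of 7 days. If it has fallen, "If calcium levels return to below 10.2 mg/dL, daily injections will be reinstated and quarterly calcium checks will be performed."
- **Above 11.0 mg/dL:** "If serum calcium is greater than 11.0 mg/dL, treatment will be withheld for two weeks at which time serum calcium will be rechecked." Then, "If it is between 10.2 and 11.0 mg/dL we will reinstitute treatment at the reduced frequency of 5 of 7 days per week." If it is still above 11.0, the patient is referred and leaves the study.

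For calcium below 8.5 mg/dL on cinacalcet, the same section stops treatment for two weeks and excludes the patient if calcium is still low. Otherwise, "If calcium is normalized, cinacalcet will be reinstated at half of the prior dose. Calcium will be checked again at the next monitoring visit." Safety Precautions, in its teriparatide paragraphs, says instead that treatment ceases and the patient is excluded.

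Between visits, Safety Precautions provides: "Monthly telephone or personal contact will be made by the study coordinators to the patients in order to monitor possible adverse events or reactions."

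**The concern.** A calcium that is acceptable on five injections a week does not directly show what it will be on seven. Seven a week is the schedule on which this patient's calcium first rose. The plan itself treats the start of teriparatide and a reduction in its frequency as reasons for an early calcium check, yet the return to full frequency has none. A second rise without symptoms could go unmeasured by the study until the next scheduled visit.

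Two neighbouring rules raise related questions. After a hold for calcium above 11.0, the plan gives no action for a result below 10.2, which is the result the hold is meant to produce. For low calcium on cinacalcet, two sections dispose of the same patient differently.

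**Working it through.** The plan gives no figure for this interval, so there is none to reproduce. The check is calendar arithmetic, followed by setting the rules side by side.

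**Inputs.** From Treatment Protocol for Teriparatide: 20 µg per injection; 7 or 5 injections a week; recheck at 14 days, window 11 to 17. From Table 2: biweekly visits until steady state, then fixed quarterly visits. One quarter is 52/4 = 13 weeks = 91 days.

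**Weekly dose.** At 5 of 7 days: 20 × 5 = 100 µg. Daily: 20 × 7 = 140 µg. The increase is 140/100 − 1 = 40%. The single dose stays at 20 µg.

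**Gap to the next scheduled calcium.** Count from the day the raised value was found. Gap = day of next scheduled draw − day of recheck.

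- Biweekly visits still running, next visit at day 28: 28 − 14 = 14 days, or 2 weeks (28 − 17 = 11 to 28 − 11 = 17 days).
- Found at a quarterly visit, next visit at day 91: 91 − 14 = 77 days, or 11 weeks (91 − 17 = 74 to 91 − 11 = 80 days). That is up to 77 daily injections before the next scheduled calcium.
- The gap can be shorter near a fixed visit. If the value is found at day 70 of treatment, rechecked at day 84, and Q1 falls at day 91, the gap is 7 days.

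**Comparison with stable patients.** In the quarterly phase a stable patient's next draw is also at day 91. The affected patient has the day-14 recheck in addition. The scheduled interval is therefore no longer than for others; what is absent is a draw triggered by the increase.

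**What triggers a calcium check.**

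- First teriparatide dose: yes, 1 week +/- 3 days.
- Reduction to 5 of 7 days: yes, 2 weeks +/- 3 days.
- Hold for calcium above 11.0: yes, at two weeks.
- First alendronate dose: yes, 1 week +/- 3 days.
- Return to daily teriparatide: none; only quarterly checks are named.
- Restart of teriparatide after a hold: no specific check is stated.
- Half-dose restart of cinacalcet: at the next monitoring visit.

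**Actions after a hold for calcium above 11.0.** Still above 11.0: exclusion. 10.2 to 11.0: restart at 5 of 7 days, from 0 to 100 µg per week. Below 10.2: no action is stated in that rule.

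**Calcium below 8.5 on cinacalcet, normal again after two weeks.** Research Procedures: restart at half dose. Safety Precautions: out of the study. Both cannot be followed.

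**Limit of the check.** The calcium row of Table 2, as extracted, has 12 marks against 10 readable columns, and the attached Research Procedures figure is not visible. An extra fixed draw could shorten these gaps, but it would not be tied to the return to daily dosing.

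**The case against.** The case for leaving the text alone is substantial.

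- **The clearing value is taken at an unfavourable moment.** Blood is drawn the morning after a full 20 µg injection. This stands and narrows the contrast between the two frequencies, but it does not reproduce seven consecutive days of dosing.
- **Early in treatment the gap is short.** A patient whose frequency was cut and restored within weeks is hard to call steady, and nothing withdraws that patient from the biweekly visits. A reader might infer a wait of 8 to 10 weeks until Q1 after an excursion found at weeks 1 to 3. That requires reading the quarterly phrase as cancelling those visits, and the more natural reading is about 2 weeks.
- **Thirteen weeks is not supported.** A reader might count a full quarter from the day daily dosing resumes. Table 2 lists fixed visits, and no text restarts the calendar, so about 11 weeks is the supported upper figure.
- **Other safeguards continue.** Monthly contacts and the symptom rules in Safety Precautions remain, and Research Materials, Records and Privacy records serum calcium from medical records. None of these requires a calcium draw, and the records carry no stated frequency or link to dosing.
- **The jump from no drug to daily dosing is not prescribed.** A reader might infer that a patient held for calcium above 11.0 who falls below 10.2 goes from 0 to 140 µg per week. That comes only from borrowing a sentence written for the 5-of-7 recheck. What the documents show is a missing instruction.
- **The cinacalcet conflict is a different matter.** It concerns another drug and the opposite direction of calcium. It is real, but it adds nothing to the point about daily teriparatide.

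**Conclusion.** The point holds in a limited form. The plan returns a patient from 100 to 140 µg per week on a calcium measured at the lower frequency, and no calcium check is triggered by the increase. The next scheduled draw is about 2 weeks away if biweekly visits are running and about 11 weeks away if the excursion was found at a quarterly visit.

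These figures assume a 13-week quarter, Table 2's visits kept on their calendar, and biweekly visits that continue for a patient not yet at steady state. They are subject to the unreadable part of Table 2 and the unseen figure.

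The two linked points also stand: no action is stated for calcium below 10.2 after a hold for a value above 11.0, and two sections conflict on calcium below 8.5 with cinacalcet.

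The number of patients affected is not given and is probably small; the plan itself calls the cinacalcet case rare. A reader might infer that affected patients are followed less closely than stable ones, or that the one-year QCT comparison is at risk. The documents support neither. This is an inexpensive safety clarification.

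**What to change.** 1. In Treatment Protocol for Teriparatide, add one calcium check 1 week +/- 3 days after daily injections resume, and after any restart following a hold; then return to the existing visit schedule. The first check then falls at 4 to 10 days. Adding biweekly draws until steady state is not needed and could cost several draws per patient.
2. State that a calcium below 10.2 mg/dL after a hold for a value above 11.0 leads to restart at 5 of 7 days per week, with daily dosing only if calcium stays below 10.2 on that frequency.
3. Bring the cinacalcet sentence in Safety Precautions into line with Research Procedures: hold for two weeks, restart at half dose if calcium is normalized, exclude if it is still below 8.5.

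The cost is wording in two sections and about one extra calcium draw per affected patient. The serum biochemistry paragraph under Study Design already allows dialysis staff to take blood during treatment. Endpoints and sample size are untouched.
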